related questionnaires in our feasibility trial. Based on our feasibility trial, symptom reporting takes about 10 minutes to complete. The remainder of the assessment tools will either be collected only at the 3-month follow-up and the 6-month follow-up or baseline, 3-month follow-up, and 6-month follow-up. Completion of all surveys takes about 30 minutes (see Table 6 and the Appendix for details on the surveys). The UCSF School of Nursing Symptom Management Model (The University of California, 1994) is based on the premise that effective management of symptoms demands that three dimensions are considered: Symptom Experience, Self-Care Symptom Strategies, and the Outcomes (Dodd et al., 2001). The interrelatedness of these three dimensions of symptom management is not consistently taken into account in research (Figure 5) (Lenz, Pugh, Milligan, Gift, & Suppe, 1997).

Outcome Measures for Aim 2 RCT is listed in Table 3 below:

Primary outcome: The primary purpose of the intervention is to improve symptom status. We hypothesize that VIP-HANA will improve symptom frequency and intensity, our primary outcomes.

Secondary outcomes: The potential benefits of the intervention are quite broad, so multiple secondary outcomes are of interest (see Table 3). As a result of improving symptom status and frequency among PLWH, several other factors that contribute to a subject's overall well-being may be affected. Changes in symptom status should have an effect on secondary health outcomes including quality of life, frailty, adherence to ART, and system use. Importantly, symptom burden has been identified as a predictor of ART adherence (Gay et al., 2011). Unlike treatments for other illnesses, ART medications are more likely to contribute to greater discomfort and treatment discontinuation (Chesney, Morin, & Sherr, 2000). As a result it is not surprising that only 25% of PLWHA in the US are virally suppressed. Therefore symptom management is of critical importance for improving clinical outcomes in PLWHA and of public health importance (Services, 2014).

Table 3. Outcome Measures		
Outcomes	Tool	Collection Time
Primary: Symptom Status	The revised Sign and Symptom Check-List for HIV (SSC-HIVrev)([name], Hudson, Kirksey, Hamilton, & [name], 2001)	Every 1 week
Secondary Outcomes		
Quality of Life	Medical Outcomes Study Standard Form (SF 12) (Ware, Kosinski, & Keller, 1996)	Week 0, 3-month follow-up, 6-month follow-up
Engagement with Health care Provider	Engagement with Health care Provider Scale ([name] et al., 2000)	
		Number of healthcare visits

CD4, Viral Load	Clinical outcomes	Abstraction
ART Adherence	Visual Analogue Scale Self-report (VAS) (Arnsten et al., 2001; Chesney, Ickovics, et al., 2000; De Costa et al., 2010; Walsh, Mandalia, & Gazzard, 2002)	Week 0, 3-month follow-up, 6-month follow--up
Frailty	Fried's Frailty Phenotype (Brothers et al., 2014; Fried et al., 2001); Used in numerous HIV-related studies (Desquilbet et al., 2007; Desquilbet et al., 2009; Piggott et al., 2013)	
System Use	Log Files	Automated

We are paying particular attention to the symptom experience of the study participants over time, the components of the symptom management strategies (e.g. content and frequency of use) through log files, and symptom status as our primary outcome but multiple secondary outcomes are also of interest. Of particular relevance, one of the assumptions of the model is that once symptoms have been successfully addressed then the secondary outcomes should show improvement. Findings from our RCT will inform this hypothesis.

Data Management and Analysis: All survey data will be stored on a secure server. All multivariate analyses will be preceded by standard descriptive statistics to profile participants in each study group and to examine distributions of all outcome variables and to identify outliers. Descriptive statistics (i.e., means, standard deviations, frequencies, and percentages) will be used to examine demographic characteristics of the sample and the frequency and intensity of the symptoms. We will use intention-to-treat principles for the primary outcome analysis.

Intention to treat implies all subjects are considered in analyses. Linear mixed model and generalized linear mixed model (negative binomial model) will be used for the analysis of symptom intensity outcomes and symptom frequency outcomes, respectively. Linear and generalized linear mixed models are statistical models that are particularly well suited to analyze repeated measured symptom data. This method does not require equal waves of data and allows missing outcome measures during the course of the study. This is an attractive method for longitudinal analyses, where participant attrition can be a problem, because participants often drop out and return for later follow-up or drop out entirely. Therefore, it is useful in retaining power in statistical analyses. The mixed models incorporate correlation between the reports of symptoms as these reports are measured from the same subject repeatedly over time and can account for this correlation for the model inference (Ugrinowitsch, Fellingham, & Ricard, 2004). An assumption for using linear and generalized linear mixed model methods is that the cases missing to subsequent follow-up assessments are missing at random. If missing data is related to intervention assignment or symptom outcome, we will estimate the probability of not missing a data point (i.e., the probability of reporting symptom) and include the inverse of this probability in the model as a selection weighting factor to correct for bias due to missing data.

For analysis of secondary outcomes, if the outcomes are measured more than once, we will use

linear and generalized linear (logistic or negative binomial model) mixed model. If the outcomes are measured only once, we will use linear or generalized linear model. We will also assess any net benefits in the patients' report of their healthcare provider's engagement with their treatment and care, quality of life, frailty, ART adherence and biological outcomes (CD4 and viral load). Analysis of additional hypotheses includes assessment of differences in the self-care strategy used to help alleviate a symptom and the recorded level of intensity following the strategy use will also be assessed. Based on the Symptom Management Model, we anticipate that VIP-HANA will be effective at improving symptom status and then we will see a positive change in our secondary outcome measures: quality of life, frailty, ART adherence, and CD4/ viral load.

Specific Aim 3: Understand PLWHA's perceptions of the predisposing, enabling, and reinforcing factors for VIP-HANA use with theoretically-guided focus group sessions.

The goal of these focus group sessions is to understand the experience of PLWHA using the VIP-HANA system. The adaption of this model for HIT was originally developed by Kukafka et al. (2003). [name] has used this model in previous studies to understand the barriers and facilitators to implementation of health information technology systems ([name], Clark, Olender, & Sperling, 2013; [name], Gordon, Camhi, & [name], 2011). If VIP-HANA is found to be efficacious in our trial, then our follow-up focus groups will inform dissemination and implementation of the VIP-HANA intervention. If the intervention is not efficacious then we will learn why participants did not find the intervention to be useful or improve their outcomes.

Sample: Post-intervention, we will conduct five focus group sessions with approximately 6-12 participants per group. Focus group participants will be drawn from the VIP-HANA group (intervention arm) and the attention control group. We anticipate that 60 participants will agree to participate in the follow-up focus groups.

Procedures: The focus groups will be 60-90 minutes in length. We will include \$30 reimbursement for participants' time. Following completion of the informed consent process, all focus group sessions will be audio-recorded. The PI, who has conducted focus groups for a number of studies in the past, will convene the groups with the study participants and will act as a facilitator (Lee et al., 2011; Okoniewski, Lee, Rodriguez, [name], & Low, 2013; [name] et al., 2013; [name], Kaufman, et al., 2009; [name], Odlum, Gordon, & [name], 2009). The focus group guide will be informed by the Predisposing, Reinforcing, and Enabling Constructs in Evaluation (PRECEDE) portion of the PRECEDE- PROCEED Model of health program planning and evaluation (Green, Kreuter, Deeds, & Partridge, 1980). The integration of these frameworks for application in HIT implementation evaluation has been proposed by a number of authors as a strategy for assessing predisposing, enabling, and reinforcing factors for use and acceptance of HIT (Kukafka et al., 2003; [name] et al., 2011). Sample focus group questions are: 1) Describe your use of the VIP-HANA system 2) What are some of the ways that your overall health benefited through the use of the VIP-HANA system (reinforcing factors)? 3) What were the barriers to your use of VIP-HANA in your everyday life? (predisposing factors) 4) What are your ideas about strategies for overcoming these barriers? (enabling factors) 5) What did you perceive as useful about the VIP-HANA system? (predisposing factors) 6) How would you envision VIP-HANA being used in your everyday life? (implementation) 7) How do you imagine that VIP-HANA would be shared with others PLWHA? (dissemination) 8) Any other thoughts about your experience using the VIP-HANA system that you would like to share?

The team will adhere to qualitative research processes to ensure the credibility, confirmability, dependability and transferability of the qualitative data from these analyses. To support

the credibility of the data, we will conduct peer debriefing and triangulate findings across multiple data sources (surveys, focus group data). In addition, we will use “member checks,” i.e., sharing of initial data interpretations with participants, to ensure accurate interpretations.

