Specific aim 1a: Identify the most prevalent symptoms and self-care strategies of PLWHA with HANA conditions in order to modify the VIP system into the VIP-HANA system. We will also include PLWHA without HANA conditions for a comparison analysis. In response to the reviewers' feedback, we have completely revised Aim 1 so that we can collect the best patient-reported evidence that is available. The goal of our work in Aim 1a is to identify the most frequently reported symptoms and self-care strategies of PLWHA with HANA conditions and integrate them into our existing VIP system. We will expand and refine the existing symptom list (21 symptoms) to include symptoms and self-care strategies by adding new symptoms that are the most frequently reported by survey participants with HANA conditions in Aim 1. The additional information that is collected will be synthesized and incorporated into the VIP system which will result in the VIP-HANA system. **The VIP-HANA system will deliver self-care strategies to PLWHA with HANA conditions tailored to symptom reporting, HANA condition(s) and gender.** VIP-HANA will be a web-application (app) and can be used on a computer or a mobile device.

Online Survey with 2,000 PLWHA:

This web-based survey will enroll approximately 1,000 PLWHA with HANA conditions and approximately 1,000 PLWHA without HANA conditions into an anonymous online survey that inquires about symptoms and self-care strategies of PLWHA with HANA conditions. Study participants will be recruited online from various social media sites such as Facebook.com (the largest online social networking site) and POZ (poz.com). [name] (Co-I) has had great success using this recruitment strategy (Chiasson et al., 2005; Hirshfield, Remien, Humberstone, Walavalkar, & Chiasson, 2004; Hirshfield, Remien, Walavalkar, & Chiasson, 2004).

Eligibility criteria: 1. HIV+; 2. Age 18 or over; 3. Able to read and respond in English; 4. Reside within the US; 5. Willing to participate in an online survey. We have chosen the following HANA conditions because they are the most frequently occurring conditions that result in mortality and/or morbidity (Crothers et al., 2006; A. Justice & Falutz, 2014; A. C. Justice, 2010; A. C. Justice, 2014; A. C. Justice et al., 2004; Kendall et al., 2014; Messeri, Lee, & Berk, 2009; So-Armah & Freiberg, 2014).

HANA Conditions: Cardiovascular Disease, Liver Disease, Asthma, Bronchitis, COPD, Osteoporosis, Diabetes, arthritis and/or Renal Failure

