Study banners will be created by Public Health Solutions for recruitment of PLWHA with HANA conditions for the aforementioned survey. The study banners will route people to our study landing page. We conservatively estimate that at least 50% of all PLWHA in the US suffer from at least 1 HANA condition based on our review of the literature (Crothers et al., 2006; A. Justice & Falutz, 2014; A. C. Justice, 2010; A. C. Justice, 2014; A. C. Justice et al., 2004; Kendall et al., 2014; Messeri et al., 2009; So-Armah & Freiberg, 2014). Given this estimate, of the 150,000 PLWHA who use POZ.com as well as additional PLWHA with HANA conditions who use Facebook, we should easily be able to collect our study data within our study timeframe. [name] collaborated with POZ on a brief online pilot in NY, CA and GA, sending emails to a defined subset of HIV+ male members identifying as gay or bisexual (n=5,262). POZ's email system can target members by location, sexual orientation, race/ethnicity, age, and most recent log-on. Of the 5,262 emailed, 1,696 (32%) clicked through; 479 of those who clicked through consented (28%); and 464/479 completed the survey (97%). In 7 days, through direct email with POZ Personals members, we were able to collect 463 completed cases. For the proposed study, we will be using banner ads on POZ and may not have the same response rate; however, 4 months is a sufficient amount of time to recruit 1,000 participants, given our inclusion criteria.

During the initial stages of survey collection for Aim 1a we detected a significant gender disparity in our population being mostly males completing the survey. Due to this difficulty recruiting women, in an effort to increase the number of female participants we will close the enrollment for males at this time. We have modified our survey to include female reproductive system questions and created a recruitment flyer offering \$10 as an incentive for female survey takers. A new survey has been created for this purpose.

See Attachment: VIP HANA Women Qualtrics Survey.pdf

For this purpose, we will launch a paid online campaign through POZ.com as well as flyers posted around the Columbia hospital and surrounding areas as well as other social media sites to include more women and reduce gender disparity. Online female survey takers will receive a \$10 amazon gift code while on site female survey takers, recruited through posted flyers, will receive \$10 in cash.

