Procedures: PLWHA who click our banner advertisements posted online will be automatically

directed to a study landing page that will screen to see if they qualify for participation. If they do qualify then they will be directed to complete the consent form. Those who consent, by clicking a consent button, will then complete a one-time only anonymous online survey. Employing the methods used by [name] (consultant) and [name] (Co-I) when they originally developed the HIV Symptom Self-Management Manual ([name] et al., 2000; Corless et al., 2002), participants will be asked to identify the 3 most disruptive symptoms they experienced in the past month.

Survey questions related to Symptoms and Self-care strategies are in Table 4. The web-based survey will be hosted by Qualtrics software. Columbia University Medical Center has a license with Qualtrics and all data collected through this software is HIPAA compliant. Qualtrics is also CUMC-certified and PHI secured which is a requirement of the Columbia University IRB for data collection via the Internet. Qualtrics will automatically assign random subject ID#s to each participant. We will collect information on symptom reporting and self-care strategies. Data will also be collected regarding additional secondary measures such demographics, psychosocial measures, ART adherence and scheduled/missed healthcare visits. As we mentioned before we will include PLWHA without HANA conditions for a comparison analysis. At this time we have decided to close the enrollment for males and direct more efforts into including female participants.

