Data Analysis: Frequency of symptom reporting will be calculated. Our analysis will look for differences in symptom reporting and self-care strategies based on HANA condition, age and/or gender. We anticipate that there will be differences in gender but not in age (See Section C.2.1 below). Symptoms must be attributed to a HANA condition to be included as part of the final list of symptoms in our intervention. We anticipate that some self-care strategies will be the same for different conditions. In other cases, strategies will be different and the VIP-HANA system will deliver a self-care strategy tailored to symptom reporting, HANA condition(s) and gender, if applicable. Content analysis will be used to analyze the self-care strategies and attribution data for inductive development of the category schemes. Initial codes or categories of self-care strategies will be identified inductively from the data. To reduce the number of categories, initial codes will be consolidated on the basis of theoretical similarities and clinical significance after consultation with our study team. Drs. [name], [name], [name] and the research assistant will collaborate on this analysis. We will also categorize the self-care strategies by information source reported by the survey respondent. Strategies which are potentially harmful or illegal (e.g., substance use) will not be included in VIP-HANA. We will have precautions in place to advise patients who appear to be at-risk for negative outcomes (e.g., report of severe depression) to contact their healthcare provider, call 911 or go directly to the emergency room.

Study Team and Experts will finalize the symptom list and self-care strategies: In year 2, we will conduct a meeting with the study team and the EAB to finalize the symptom list and the self-care strategies to be included in the VIP-HANA system. Once this has been finalized, technical refinement of our existing web app will take place at CBITs (see facilities and resources). We have partnered with CBITs since they use Purple, an extensible, modular, and re-purposable system created for the development of Web-based and mobile-based applications for health behavior change (Schueller, Begale, Penedo, & Mohr, 2014). [name] (PI: CBITs) is the Site PI for this project. Figure 4 illustrates a sample screen created by CBITs of self-care strategies for depressive symptoms. In response to the reviewer's request, a letter of support

from the technical team is included.

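### Aim 1a's pooled gender comparison, which informs gender tailoring, is partly confounded with survey version, recruitment route, payment and calendar time

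*Combined protocol and SAP*

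**What the plan says.** All references are to the combined protocol and SAP, Specific Aim 1a, unless stated otherwise.

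- **First wave.** Recruitment describes an online survey open to both genders through two online venues. Early on, "we detected a significant gender disparity in our population being mostly males completing the survey".
- **Closure to men.** Recruitment states "we will close the enrollment for males at this time", and Procedures repeats it: "At this time we have decided to close the enrollment for males and direct more efforts into including female participants".
- **Second wave.** "We have modified our survey to include female reproductive system questions", and "A new survey has been created for this purpose". Women are recruited by a paid POZ.com campaign, other social media, and flyers in and around the hospital. Online women receive a $10 gift code; women who respond to the flyers and complete the survey on site receive $10 in cash.
- **Other payment.** The table of target enrollment and compensation also mentions $10 for those who took a follow-up survey online, without naming a gender.
- **Analysis.** "Our analysis will look for differences in symptom reporting and self-care strategies based on HANA condition, age and/or gender". The same paragraph says in advance that gender differences are expected. Table 1 describes the Aim 1a analysis as descriptive and thematic.
- **Use.** VIP-HANA strategies are to be "tailored to symptom reporting, HANA condition(s) and gender". The Data Analysis paragraph limits gender tailoring to cases where it applies.

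No section stratifies or adjusts by survey version, route, payment or date, or limits the gender comparison to people who took the same survey.

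**The concern.** After closure, no man can appear under the second-wave conditions. Four things change for the women who enter then: the questionnaire, the payment, part of the recruitment route, and the calendar period. Any of these can move symptom reporting without a gender effect. For example, Procedures asks each respondent to name the three most disruptive symptoms. With three places to fill, reproductive prompts could push out general symptoms among women even if the core items are the same. That is a plausible mechanism, not a demonstrated one, because the survey attachments are not part of the document.

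At stake is what the gender contrast is used for. A difference produced by survey conditions could be taken as a gender difference and built into the tailored content, which Table 2 shows to be what separates the trial arms. Because the protocol already expects gender differences, an artefact is less likely to be questioned.

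**Working it through.** The documents give no sample size, test or error rate for the gender comparison, so there is no planned figure to reproduce. The check has two parts.

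**1. Which conditions overlap between men and women**

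| | Men (all first wave) | First-wave women | Second-wave women |
|---|---|---|---|
| Questionnaire | original | original | new, with reproductive items |
| Route | online | online | paid online campaign, social media, flyers; some on site |
| Payment stated | none, apart from the follow-up survey | none, apart from the follow-up survey | $10 |
| Period | before closure | before closure | from closure on |

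The first two columns can be compared like for like. The third has no male counterpart. A first wave described as mostly male implies some first-wave women, but no count is given.

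**2. Scale, by illustration**

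Assumptions, none of them from the documents: no true gender difference; 700 men and 300 women; 30% of first-wave respondents report a given symptom; second-wave conditions shift reporting by s; a share f of the women is first wave.

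Bias in the pooled female-minus-male difference = (1 − f) × s.

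The chance of a significant result uses a two-sided 5% test of two proportions, which the plan does not specify. With d = (1 − f) × s, women's rate p_w = 0.30 + d, and pooled rate p̄ = (700 × 0.30 + 300 × p_w)/1000:

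- SE0 = √[p̄(1 − p̄)(1/700 + 1/300)]
- SE1 = √[0.30 × 0.70/700 + p_w(1 − p_w)/300]
- chance = Φ[(d − 1.96 SE0)/SE1] + Φ[(−d − 1.96 SE0)/SE1]

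Worked case, f = 0 and s = 0.10: p_w = 0.40, p̄ = 0.33, SE0 = 0.0324, SE1 = 0.0332. Then (0.10 − 0.0636)/0.0332 = 1.10, so the chance is 0.86; the second term is negligible.

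| First-wave share f | s = 5 points: bias, chance | s = 10 points: bias, chance |
|---|---|---|
| 0 | 5.0 points, 35% | 10.0 points, 86% |
| 0.25 | 3.75 points, 22% | 7.5 points, 64% |
| 0.50 | 2.5 points, 13% | 5.0 points, 35% |

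Using SE1 in place of SE0 gives values about one point lower (34% and 85% in the first row). With a 2-point shift and f = 0 the chance is about 10%.

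**Precision of the like-for-like contrast.** The 95% half-width is 1.96 × √[0.30 × 0.70 × (1/700 + 1/n)], where n is the number of first-wave women. For n = 150 it is 8.1 points; for n = 75 it is 10.9 points. With all 300 women pooled it would be 6.2 points, but with the bias above.

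**The case against.** Several counter-arguments have force.

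- **No test is planned.** The analysis is descriptive and thematic. A reader might take 35% to 86% as the plan's false-positive rate; the documents do not support that. The test, base rate, gender split and shift are all assumed, and the upper row also assumes that every woman is second wave. This objection stands. A descriptive reading nevertheless carries the same bias, (1 − f) × s.
- **Gender and wave are not inseparable.** A reader might infer from the male closure that they are. The account of the first wave implies that some women took the original survey. This stands, and it makes a same-survey contrast possible.
- **The questionnaires may differ little.** The only stated change is the added reproductive items. Nothing shows that core items changed, and nothing shows that they did not.
- **Payment is not wholly tied to gender.** The follow-up survey also carried $10, with no gender named. This stands.
- **Harm is not automatic.** Symptoms must be attributed to a HANA condition, codes are consolidated on theoretical similarity and clinical significance, and the study team and advisory board settle the content. The one gender-marked item in the Aim 2 symptom list, erectile difficulty, is sex-specific. A reader might infer that strategies will be withheld from one gender; the strategy content is not shown, so this can be neither confirmed nor excluded. Nothing says, however, that those deciding will see results by survey version.
- **Local recruitment may be relevant.** Aim 2 recruits across New York City, so flyer-recruited women may resemble the eventual users. That helps relevance but does not make them comparable with men recruited online.

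**Conclusion.** The concern holds in a limited form. As written, the pooled gender comparison is partly confounded with survey version, route, payment and time, and no section deals with this. The direction and size of the bias are unknown. They depend on the first-wave share of women and on how far second-wave conditions change reporting, and the documents give neither. Under the assumptions shown, the spurious difference is 2.5 to 10 points.

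A reader might also infer that the Aim 2 result is compromised. It is not: allocation is randomized, and this issue affects what the app contains, not the comparison of arms. The consequence is confined to Aim 1a inference and to the evidence behind gender-tailored content. Recruiting more women was reasonable and need not be undone. This is a low-cost improvement to the analysis.

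**What to change.** Add to the Aim 1a Data Analysis paragraph:

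1. Report gender differences by survey version, using only items common to both questionnaires.
2. Compare first-wave with second-wave women on those items before pooling, and report that difference.
3. Show the original-survey contrast of men and women beside the pooled contrast, and break results down by route (online or on site) where it was recorded.
4. Treat a gender difference that is not sex-specific as a basis for tailoring only if the original-survey contrast points the same way. Otherwise disclose it as possibly due to survey conditions.

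The cost is analysis wording and some extra tables. The separate surveys should make version identifiable, but the survey is anonymous and the documents do not say that route or incentive was stored for each respondent, so the sponsor should confirm what is available. The main drawback is precision: the same-survey contrast rests on the small group whose scarcity prompted the change, so both contrasts should be shown with intervals.

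The document is dated April 2018, cites usability materials from May 2017 and already lists the symptoms for Aim 2, so the app content may be final. If it is, the same steps apply as a re-analysis and a disclosure when Aim 1a is reported.
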